## 3 Study Design

### 3.1 General Design

Patients will be identified and enrolled from Thoracic Surgical Clinics. Patients will undergo surgical resection with the collection of tumor tissue, normal lung tissue, blood, and skin biopsies. For patients enrolled in the study that were found to have stage IA-IIIA SCC, starting less than 90 days from the time of surgery, patients will be randomized to receive either 850 mg po BID of metformin or observation. Metformin dosing will include a 4 week ramp up of 850 mg po daily prior to starting the BID dose, for a total of 6 months of Metformin. Patients will be followed for 2 years from the time of surgery to evaluate 2-year RFS. We plan to randomize a total of 100 patients (50 per arm), such that 90 patients are evaluable for the primary endpoint.

### 3.2 Embedded Correlative Studies

Patients will be enrolled in the correlative studies as the volume of tissue permits.

1. Derivation of fibroblast cultures from skin biopsy samples.

Skin biopsies will be taken at the time of surgical resection. Biopsy samples taken in surgery will be taken as a 2mm x 2cm excision of a wedge of skin at the edge of the incision. Such excisions are frequently done as part of routine skin closure for optimal skin cosmesis following surgery. Samples are transported to the laboratory, and the epidermis and hypodermis removed. The dermis is cut into small pieces ( $<2\text{ mm}^2$ ) before plating in each well of a 6-well plate along with Dulbecco's modified Eagle's medium supplemented with 10% fetal calf serum, 1% L-glutamine and 1% penicillin/streptomycin. Within an average of nine days, dermal fibroblasts are visible by light microscopy.

2. iPS cell reprogramming from skin fibroblasts.

For defined metformin “responders” and “non-responders”, iPSCs will be generated. We plan to create a total of 50 iPSC cell lines for subsequent in vitro differentiation and testing of metformin response. Fibroblast cell lines are plated at  $10^5$  per 24 wells then transduced with infectious supernatants bearing the stemness factors OCT3/4, SOX2, KLF4 and c-MYC25. Transduced fibroblasts are re-plated at confluence and iPS cells isolated after two weeks of clonal expansion. Cells are assessed by phase contrast microscopy for morphologic characteristics of iPS cells. iPS cell reprogramming will be performed in conjunction through the Regenerative Medicine Biotrust with our commercial partner ReGen Theranostics.

3. Evaluation of genomic alterations in histologically normal airway epithelium, pre-invasive lesions of lung SqCC, and invasive SqCC.

DNA from biopsy specimens will be evaluated for DNA quantity and quality and subjected to mutation analysis using our panel of known genes. DNA will be prepared using standard protocols. A number of samples will also be used for exome sequencing as DNA quantities and funding permit. Data will be analyzed for the presence of mutations not present in germline DNA obtained via a blood sample. Mutation profiles will be compared between all patients receiving metformin versus placebo and correlated with clinical outcome. The subject will give a 4ml blood sample (collected in EDTA tube) to be used as normal comparative sample of DNA.

4. Biospecimen banking of blood, normal lung, lung tumor, and skin biopsy specimens and derivitives.

All patients participating in the trial will be provided an opportunity to participate in Biospecimen banking for the correlative studies described above and future studies.

Samples will be stored in the Mayo Clinic Lung Specimen Registry, Regenerative Medicine Biotrust repository, or in [name] Oncology Laboratory.

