Phase I/II studies directed toward effects on existing tumors or pre-invasive lesions with surrogate endpoints have shown promise, but may not translate to real effects on the histologically normal tissue and cell types that are the true targets of chemoprevention. Our recent in vitro data indicating heterogeneity in metformin response suggest that all patients may not respond equally to its potential chemoprevention effects. The preliminary data to be gathered in the proposed pilot study will be critical to evaluate the feasibility of performing a randomized, phase III trial addressing this question as an Alliance study through the cooperative group infrastructure. The pilot data will also serve as important preliminary data for a correlative studies R01 grant in conjunction with a larger trial, with aims of evaluating the effects of metformin on patients with resected Stage IB-IIIA NSCLC, creating cohorts of metformin responders and non-responders based on disease recurrence, and finally generating iPS cells for in vitro studies and development of a metformin response index. This pilot trial will also address an under-represented area (lung cancer) in the Alliance Prevention Committee portfolio.

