## 2 Study Objectives

Primary objective for pilot study:

1. To evaluate the feasibility of patient randomization, accrual, and tissue collection in a pilot study of metformin versus observation following resection of stage IA-IIIA lung squamous cell cancer for patients.
2. To compare the 2-year recurrence free survival (RFS) rate between metformin and observation.

[figure not shown]
Secondary objective(s) for pilot study:

1. To develop the metformin sensitivity index based on iPS cell lines from the first 20 patients randomized to the metformin arm.
2. To apply the metformin sensitivity index on the remaining 25 patients randomized to metformin and the 45 observation patients (70patients total) to compare the 2-year RFS rate between metformin-sensitive and metformin-not-sensitive patients
3. To compare adverse events between metformin and observation arms using CTCAE version 4.

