## 7 Statistical Plan

### 7.1 Statistical Methods

All patients meeting the eligibility criteria, and who started treatment, will be considered evaluable for the 2 year RFS rate endpoint. The proportion of 2 year RFS rates (along with the 95% confidence interval) will be estimated within each arm by the number of patients who are recurrence-free and alive at 2 years divided by the total number of evaluable patients in each arm, and compared using a chi-squared test.

Clinical data regarding recurrence-free survival (RFS) will be utilized for development of the metformin sensitivity index. Data collected will be summarized using descriptive statistics, including mean and standard deviation and median and inter quartile range for continuous variables, and using frequencies and percentages for categorical variables. Logistic regression models will be used to assess the impact of metformin sensitivity index metrics, treatment, and the interaction between the metformin sensitivity index metrics and treatment on the 2 year RFS status as the outcome of interest.

Adverse events (AEs) will be compared between metformin and placebo using CTCAE version 4. To evaluate the AE profiles associated with each intervention arm, the maximum grade for each type of AE will be recorded for each participant and frequency tables will be reviewed to determine the overall patterns. The number and severity of AEs (overall and by intervention group) will be tabulated and summarized across all grades. Chi-square tests will be used to compare the AE rates between metformin and placebo.

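### Section 3.2 makes 50 iPS lines for patients already labelled responder or non-responder, section 2 needs 90 by arm and randomisation order, and nothing masks the index call to recurrence or arm

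*Combined protocol and SAP*

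**What the plan says.** Four places in the combined protocol and SAP bear on who gets an iPS line and how the index is formed.

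- **Section 3.2, item 2:** "For defined metformin “responders” and “non-responders”, iPSCs will be generated". It continues: "We plan to create a total of 50 iPSC cell lines for subsequent in vitro differentiation and testing of metformin response". The label therefore precedes the line, and the line precedes the in vitro test.
- **Section 2, secondary objectives:** the first is "To develop the metformin sensitivity index based on iPS cell lines from the first 20 patients randomized to the metformin arm". The second is "To apply the metformin sensitivity index on the remaining 25 patients randomized to metformin and the 45 observation patients (70patients total"), in order "to compare the 2-year RFS rate between metformin-sensitive and metformin-not-sensitive patients". Both sets are defined by arm and randomisation order.
- **Introduction:** among the aims of a grant tied to a larger trial is "creating cohorts of metformin responders and non-responders based on disease recurrence, and finally generating iPS cells". This is the only basis for a responder label given anywhere.
- **Section 7.1:** "Clinical data regarding recurrence-free survival (RFS) will be utilized for development of the metformin sensitivity index". The use of RFS is not confined to the first 20 patients. The index is then examined by logistic regression on 2-year RFS status, with index, treatment and their interaction.

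No section says whether the laboratory or the person classifying a patient is masked to recurrence or arm. None gives a cut-off or classification rule, a point at which the index is locked, or the timing of the assay relative to the 2-year outcome.

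**The concern.** In vitro testing follows the label in section 3.2, so the label cannot be the assay result and must be clinical. If it is recurrence, the laboratory starts from samples whose outcome is known, and secondary objective 2 then relates the index to that same outcome.

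Two separate things are at stake. The first is sampling: choosing patients by recurrence changes the RFS rates that objective 2 sets out to compare. The second is reading: with no stated cut-off, a call made with the outcome in view can drift towards agreement with it and create an association where none exists. If the reader also knows the arm, the same drift can produce a spurious interaction between index and treatment. The study has an observation control, so arm is known unless it is deliberately hidden from the laboratory.

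The Introduction presents the pilot as preliminary data for a larger trial and grant, so a false lead here would carry forward.

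**Working it through.** **1. The plan's own counts.** Inputs: 20, 25 and 45 patients (section 2); 50 lines (section 3.2); 100 randomised, 50 per arm, 90 evaluable (section 3.1).

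- Application set: 25 + 45 = 70, as stated.
- Development plus application: 20 + 70 = 90, the evaluable number in section 3.1.
- Shortfall in lines: 90 − 50 = 40. After the first 20, 50 − 20 = 30 remain, and 30/70 = 43% of the application set.

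No significance level, power or effect size is given for the index comparison, so there is no further figure to reproduce.

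**2. Can section 3.2 supply objective 2?**

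- Read literally, it cannot. Observation patients receive no metformin and so cannot be metformin responders or non-responders. The 45 observation patients would have no line.
- If the 50 lines are the 50 patients randomised to metformin, there is no outcome selection, but again no observation patient has a line.
- If the 50 are spread over the 90, some rule must choose them, and the only rule in section 3.2 is response status.

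**3. Effect of outcome selection on the rates (assumed figures).** Let true RFS be p in an index group, with two equal-sized groups and overall RFS P. If equal numbers with and without recurrence are sampled, RFS in that group becomes (p/P) / [p/P + (1−p)/(1−P)].

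- True 75% v 45%, P = 0.60. Sensitive: 1.25/(1.25 + 0.625) = 66.7%. Not sensitive: 0.75/(0.75 + 1.375) = 35.3%.
- The odds ratio is unchanged: (0.75/0.25)/(0.45/0.55) = 3.67 before and (0.667/0.333)/(0.353/0.647) = 3.67 after.
- True 80% v 60%, P = 0.70, becomes 63% v 39%; the odds ratio stays at 2.67.
- True 70% in both becomes 50% in both; no association is created.
- True 40% v 20%, P = 0.30, becomes 61% v 37%, so the direction depends on overall RFS. At P = 0.50 the rates do not move.

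**4. Effect of reading with the outcome known (assumed figures).** Take an uninformative index with half of patients called sensitive. A call disagrees with the outcome if a recurrence-free patient is called not sensitive or a patient with recurrence is called sensitive; on average half of calls do. Suppose 10% of those are changed to agree. In 70 patients that is 70 × 0.5 × 0.10 = 3.5 calls.

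With RFS 60%:

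- P(sensitive | recurrence-free) = 0.50 + 0.10 × 0.50 = 0.55; P(sensitive | recurrence) = 0.50 − 0.10 × 0.50 = 0.45.
- Apparent RFS if sensitive: 0.6 × 0.55 / (0.6 × 0.55 + 0.4 × 0.45) = 0.33/0.51 = 64.7%.
- Apparent RFS if not sensitive: 0.27/0.49 = 55.1%.
- Apparent odds ratio: (0.33/0.18)/(0.27/0.22) = 1.49, against a true value of 1. Unlike selection, this does bias the odds ratio.

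Type I error was simulated (100,000 runs per setting, uncorrected chi-squared, two-sided 0.05 assumed) at RFS 30%, 50% and 70%. Section 1.1 gives recurrence of 30-70% with no time horizon.

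| Disagreeing calls changed | n = 70 | n = 30 |
|---|---|---|
| 0% | 0.049-0.051 | 0.048-0.052 |
| 5% | 0.067-0.070 | 0.054-0.061 |
| 10% | 0.119-0.129 | 0.080-0.081 |
| 20% | 0.333-0.382 | 0.172-0.184 |

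**The case against.** The best defence is that section 2 already gives a sound rule. It assigns patients by arm and randomisation order, covers all 90 evaluable patients and does not mention outcome. Nothing says that section 3.2 overrides it. The recurrence-based label belongs to a larger study in stage IB-IIIA NSCLC, whereas the pilot takes stage IA-IIIA squamous carcinoma and never defines a responder. Skin is taken at surgery, before any outcome exists. Training on RFS in the first 20 patients is normal practice. Even deliberate sampling on outcome is a recognised design if odds ratios or weighted rates are reported, and section 7.1 does use logistic regression.

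Most of this stands, and it limits the point. A reader might infer that the RFS rates by index do come from an outcome-selected sample; that follows only if section 3.2 governs and response means recurrence. A reader might also infer that the assay is planned as open, or that responders and non-responders are run in separate batches. The documents are silent on the first and describe nothing of the second. Nor does the use of RFS in development show a flaw by itself.

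The defence does not remove the conflict. Section 3.2 is the only place that says for whom lines are made, and no reading of it yields lines for all the patients in objective 2. Objective 2 also names rates, not odds ratios. And silence on masking, where the stated procedure starts from labelled patients, leaves calls open to knowledge of the outcome.

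**Conclusion.** The point holds as a conflict between sections 2 and 3.2, together with an omission: 90 patients by arm and randomisation order against 50 lines by response status, with no masking or index lock for the 70 application patients. It should be corrected, although it affects a secondary objective of a pilot and not the comparison of arms.

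The size of any bias cannot be derived from the documents. Under the assumptions shown, equal sampling by outcome would move 75% v 45% to 67% v 35%, with the odds ratio unchanged at 3.67. Changing 10% of disagreeing calls would raise type I error at n = 70 from 0.05 to about 0.12-0.13 and, at 60% RFS, turn equal rates into 65% v 55%. The first effect depends on which section governs. The second is possible under either, wherever outcome is known when a call is made.

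**What to change.** - **Selection.** In section 3.2, replace the responder/non-responder rule with one that does not depend on recurrence and agrees with section 2. If only 50 lines can be made, take the first 20 metformin patients and choose the other 30 from the application set by randomisation order or a random draw within arm. Restate the 70 in secondary objective 2 accordingly.
- **Masking.** Code the samples, keep the laboratory masked to arm and RFS, and allocate lines to assay batches at random.
- **Lock.** In section 7.1, allow RFS to be used for building the index in the first 20 patients only. Then lock the index and its cut-off. Lock each application patient's value before it is linked to RFS. The statistical department, which already prepares the randomisation envelopes (section 5.3), could hold the link.

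**Cost.** Sample coding and a locked data transfer; no assays beyond the 50 lines planned. Lines cannot be enriched for recurrence, so fewer patients with recurrence may be among them. Keeping to 50 lines also leaves 30 application patients instead of 70. For an assumed 80% v 60% in equal groups at two-sided 0.05, power falls from 0.445 (35 per group) to 0.217 (15 per group). Keeping all 70 would need 40 more lines than section 3.2 plans.

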## 4 Subject Selection Enrollment and Withdrawal

### 4.1 Inclusion Criteria

- Suspected or biopsy proven Stage IA-IIIA lung squamous cell carcinoma (must be proven SCC at the time of surgery)
- Medically fit for surgical resection (based on surgeon assessment)
- Current or prior smoker
- Age > 18 years old
- Both Male and Female
- Willing and able to consent to study, undergo study interventions, and take study drug
- ECOG performance status 0, 1, 2
- Subject must start Metformin within 90 days of surgery.

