### **5.4 Preparation and Administration of Study Drug**

The metformin will be prepared by the Mayo Clinic Pharmacy, Research Support. At the time of the visit it will be distributed by the study team. Subsequent refills will be mailed to the subject by the pharmacy. The patient will receive dosing instruction by the study team.

[name], RPh  
Mayo Clinic Pharmacy, Research Support  
[name] or [contact]  
[[contact]](mailto:[contact])

Mayo Clinic Pharmacy, Research Support  
[name] or pager [name]  
[[contact]](mailto:[contact])

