### **6.3 Visit 3**

At the time of the subjects follow up (less than 90 days from the time of surgery) the subject will be seen by the study team. Eligibility criteria will be assessed and if the subject is still eligible they will be randomized and receive their study treatment (metformin or observation).

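### The inclusion criterion on starting metformin within 90 days applies to one arm and can be verified only after allocation, so through Section 7.1 it acts as a one-sided post-randomisation exclusion from the 2-year RFS comparison

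*Combined protocol and SAP*

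**What the plan says.** Four places in the combined protocol and SAP bear on this.

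- Section 4.1 (Inclusion Criteria): "Subject must start Metformin within 90 days of surgery". No counterpart is given for the observation arm.
- Section 3.1 (General Design): "starting less than 90 days from the time of surgery, patients will be randomized" to one of the two arms.
- Section 6.3 (Visit 3) sets the timing of the visit, "At the time of the subjects follow up (less than 90 days from the time of surgery"), and then the order of events: eligibility is assessed, and "if the subject is still eligible they will be randomized and receive their study treatment (metformin or observation").
- Section 7.1 (Statistical Methods), for the 2-year RFS endpoint: "All patients meeting the eligibility criteria, and who started treatment, will be considered evaluable".

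On drug supply, Section 5.4 says "At the time of the visit it will be distributed by the study team", and Section 5.7 has the study team give out the initial doses, with only refills mailed. Section 5.8.2 has the pharmacy dispense after it has been told the allocated arm. No section sets a maximum interval between randomisation and first dose.

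**The concern.** An inclusion criterion should apply equally to everyone who may be randomised and should be settled before allocation is known. This one does neither. Read literally, no control can satisfy it. Read sensibly, it binds the metformin arm alone and depends on something that happens after the envelope is opened.

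This would be only untidy wording if eligibility had no further role, but Section 7.1 uses eligibility to define who counts in the RFS comparison, which Section 2 lists under the primary objective. A post-randomisation event in one arm can then change that arm's denominator. The control is observation, so a decision that a patient failed this criterion would be taken with the arm known. The other part of the primary objective is feasibility of randomisation and accrual, and counts of eligible patients are less clear when one criterion is still open at randomisation.

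**Working it through.** **1. What each section times.**

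| Section | Event timed | Arms covered | Known before allocation? |
|---|---|---|---|
| 4.1 | First metformin dose | Metformin only | No |
| 6.3 | Visit with eligibility check and randomisation | Both | Yes |
| 3.1 | Randomisation or start of treatment (ambiguous) | Both, if randomisation | Depends on reading |

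The limits also differ at the boundary: the Section 4.1 wording admits day 90 itself, whereas Sections 3.1 and 6.3 do not.

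**2. When a patient is caught.** Let d be the day of Visit 3 after surgery and g the days from that visit to first dose. Section 6.3 requires d < 90. Section 4.1 fails when d + g > 90. In whole days the latest visit is d = 89, where a gap of g = 2 or more (day 91) fails. With g = 0, d + g is at most 89 and nobody fails. The visit date alone therefore excludes no one; a delay that carries the first dose past the limit is needed.

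**3. What happens to that patient.** The late starter has started treatment, so the second condition in Section 7.1 is met. The patient fails the first condition, eligibility, and is not evaluable. A control with the same d has no dose to be late with and stays evaluable.

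**4. The plan's own numbers.** Section 3.1 plans 100 randomised (50 per arm) and 90 evaluable. 90/100 = 0.90, so the implied loss is 10%, and 90/(1 − 0.10) = 100. The pair is consistent, but the document does not say what the loss consists of. It gives no alpha, power or effect size for the RFS test.

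**5. Illustrative shift.** Suppose k of 50 metformin patients are dropped for a late start and the rest are otherwise evaluable. Let p be the RFS rate in all 50 and p_late the rate in the late starters. Then

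shift = (50p − k·p_late)/(50 − k) − p = k(p − p_late)/(50 − k).

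Both k and the difference p − p_late are assumptions. For a difference of 30 points:

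- k = 1: 30/49 = 0.6 points
- k = 2: 60/48 = 1.25 points
- k = 5: 150/45 = 3.3 points

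The shift is upward if late starters do worse, downward if they do better, and zero if p_late = p. It depends on the difference and not on the level of p, so it is the same at RFS of 30%, 50% or 70%. That span mirrors the 30–70% recurrence range quoted in Section 1.1, the only overall recurrence range given there for treated NSCLC.

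**6. Precision.** At an assumed two-sided alpha of 0.05, control RFS of 50% and a 25-point difference, power is 69% with 45 per arm and 67% with 45 controls and 40 metformin patients. Loss of precision is minor.

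**The case against.** The strongest reply is that the rule will rarely catch anyone. Randomisation and hand-over of the first doses occur at the same visit, before day 90, so a metformin patient who begins promptly meets every version of the limit. Staff at that visit can also check whether a timely start is possible. This largely stands: few patients are likely to be affected. It does not remove the point. The drug is compounded, the pharmacy dispenses only once it knows the arm, patients take the capsules themselves, and no interval to first dose is stated. Checking that a timely start is possible is also not the same as verifying the criterion as written.

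Second, Section 3.1 may not conflict with Section 4.1, because the word for starting can refer to treatment. That is a fair reading. The mismatch with Section 6.3 does not depend on it.

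Third, the RFS consequence arises only through Section 7.1, whose condition on having started treatment is probably the larger asymmetry. That is also fair. But removing that condition alone would leave this route open, because the late starter did start.

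A reader might infer more: that late randomisation by itself makes metformin patients ineligible, or that the rule tilts the comparison towards metformin by removing patients who recover slowly. The documents support neither. A late visit precedes allocation and affects both arms alike. Only the gap from visit to first dose is one-sided, and nothing in the documents links that gap to prognosis.

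**Conclusion.** The point holds in a limited form. Section 4.1 contains an inclusion criterion that applies to one arm and cannot be verified at the pre-randomisation check in Section 6.3. Through the eligibility clause in Section 7.1 it becomes a post-randomisation exclusion in the metformin arm with no equivalent in controls. This follows from the text and needs no assumed figure.

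The numerical consequence is uncertain and probably small. The 0.6 to 3.3 point range rests on an assumed 1 to 5 late starters and an assumed 30-point difference in RFS. Either sign is possible, and so is zero. A large shift would need a worst case, such as every excluded patient being a future failure, for which the documents give no basis. It is worth correcting because the RFS comparison is listed under the primary objective, only 90 evaluable patients are planned, and the change costs almost nothing.

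**What to change.** Reconcile Sections 3.1, 4.1 and 6.3 into one eligibility criterion on timing. It should apply equally to both arms, be verifiable before the envelope is opened, and treat day 90 the same way throughout. State in Section 7.1 that the timing of the first dose after randomisation does not determine evaluability for the 2-year RFS comparison. Which timing limit is clinically appropriate is for the sponsor to decide.

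The cost is a few words in each section, with no added patients or visits and no change to the planned 100. The small downside is that a few metformin patients in the analysis may have started later than the limit.
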